### **2. Précis/Abstract:**

The goal of the proposed research is to determine whether riluzole, a drug that increases glutamate reuptake, will decrease CNS glutamate in breast cancer survivors with increased inflammation and fatigue. We will also determine whether decreasing glutamate with riluzole will reverse inflammation-related fatigue and other symptoms including cognitive dysfunction and decreased motivation. To accomplish these goals, we plan to conduct an 8 week, double-blind, randomized control trial of riluzole (100 mg/d) versus placebo in 40 breast cancer survivors (n=20 per group). All breast cancer survivors will have completed treatment within 1-5 years and have a fatigue level of  $\geq 4$  (on a 10 point scale) and a plasma c-reactive protein (CRP) concentration  $>3\text{mg/L}$  (indicative of high inflammation). Patients will undergo magnetic resonance spectroscopy (MRS) to measure CNS glutamate before and after 1 and 8 weeks of riluzole or placebo treatment. Fatigue and other behavioral assessments including measures of cognitive function, motivation, and startle reactivity will be conducted before and after treatment and correlated with the change in CNS glutamate.

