**Aim 2: To determine whether decreased CNS glutamate correlates with improved symptoms of fatigue and cognition dysfunction.** Behavioral assessments of fatigue and cognitive function including measures of motivation and psychomotor processing speed, attention, executive function, and memory will be assessed in the patients indicated in Aim 1 and correlated with glutamate measures in the basal ganglia and dACC as well as other brain regions as an exploratory analysis using chemical shift imaging.

**Hypothesis 2:** Decreased glutamate in the basal ganglia will be associated with decreased fatigue and improved motivation and processing speed. Decreased glutamate in the dACC will be associated with improved executive function and improved memory performance.

The proposed research will help elucidate a novel pathway to behavioral pathology in patients with breast cancer, while also identifying peripheral biomarkers of risk as well as a novel treatment.

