**+ - for patients with a CRP>3mg/L and a Single Item Screening Scale for Fatigue Score ≥4**

**\* - for patients completing the main branch of the Riluzole Study**

**\*\* - for patients who opt for to complete the Startle Test Study**

**Key:**

**Main Riluzole Study**

\*Screening/ Safety Labs: CBC w/Diff, Metabolic Panel, hCG quantitative serum, TSH, Urinalysis w/micro at Screening and Week 8 only, Urine drug test all visits (test kit), except week 2 visit; Testing for CRP, Hepatitis B and C and HIV will be conducted on the screening visit only, unless otherwise approved by the PI. A Rapid C Reactive Protein finger prick may also be obtained by trained research staff using a rapid CRP finger prick test at the discretion of the investigator to expedite determining eligibility for research participation.

\*Psychiatric Assessments: WRAT-3, MMSE, CTQ, QID-S, Single Item Screening Scale for Fatigue

\*Research Blood: Cytokine Multiplex, TRP, KYN, mRNA analysis, methylation analysis, and gene analysis (collected under fasting conditions)

\*Self-Report Forms: IDS-SR, MFI, PROMIS-Fatigue, BAI, PSQI, Assessment of Pain level, PHQ-9, Single Item Screening Scale for Fatigue, Baycrest Memory Scale

\*Neurocognitive Tests:

Baseline 1 - EEfRT, Finger Tapping Task (FTT), The Trail Making Test (TMT), Digit Symbol Task, Reaction Time Task (CANTAB)

Baseline 2 - Rey Auditory Verbal Learning Test (RAVLT), Delayed Matching To Sample (CANTAB), Spatial Working Memory (CANTAB), Stroop Color and Word Test

Week 8- EEfRT, Finger Tapping Task (FTT), The Trail Making Test (TMT), Digit Symbol Task, Reaction Time Task (CANTAB), Rey Auditory Verbal Learning Test (RAVLT), Delayed Matching To Sample (CANTAB), Spatial Working Memory (CANTAB), Stroop Color and Word Test

[figure not shown]

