#### **Self-report Forms**

**Single Item Screening Scale for Fatigue** is a single question self-report screening instrument that asks subjects to rate their fatigue on a scale of 0-10 where 0 = No fatigue and 10 = Worst fatigue you can imagine. Ratings are categorized as none to mild (0–3), moderate (4–6) or Severe (7–10). This screening strategy for fatigue is recommended by the National Comprehensive Cancer Network (NCCN) Guidelines.

**Pain assessment scale** is a Likert style self-report pain measurement (10 items; 1=no pain; 10=extreme pain) to be completed by breast cancer participants to gauge their ability to lie comfortably in the scanner. Participants reporting a current pain level of  $\geq 5$  may not be approved to participate unless otherwise approved by the P.I.

**Inventory of Depressive Symptomatology-Self Reported (IDS-SR)** is a 30-item self-report instrument with excellent psychometric properties that was designed to measure symptom constructs consistent with current psychiatric diagnostic nosology and has been widely used as a self-report outcome measure of depression in treatment trials.[32, 33] Of note, the IDS-SR is

the patient reported version of the IDS-C used in our other breast cancer study. In the event that a subject becomes unduly distressed or scores >32 on the IDS-SR (indicating moderate to severe depressive symptoms) or endorses a score >2 on the suicide item of the IDS-SR (Question 18), the PI or his designee will be immediately contacted.

**Multidimensional Fatigue Inventory (MFI)** is a 20-item scale used to evaluate the presence and severity of fatigue among subjects by self-reports.[34] The MFI assesses 5 dimensions of fatigue, including general fatigue, physical fatigue, mental fatigue, reduced activity, and reduced motivation. The MFI has been used by our group to quantify fatigue in breast cancer patients, and a minimal clinically important difference of 10 points has been established.[35, 36]

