## 10. Statistical Analysis:

**Aim 1: To study the impact of 8 weeks of riluzole treatment on CNS glutamate concentrations in breast cancer patients with increased fatigue and high inflammation.**

**Hypothesis 1:** Breast cancer patients administered riluzole will exhibit greater decreases in basal ganglia and dACC glutamate compared to women treated with placebo.

Mixed-effects models for repeated measures (MMRM) will be employed to examine effects of group, time and their interaction on left and right basal ganglia glutamate or dACC controlling for baseline glutamate concentrations in separate analyses for each brain region. Relevant covariates including age, sex, race (white/non-white) and body mass index (BMI), socioeconomic status (as measured by household income), educational status, tumor stage, tumor receptor status (where appropriate), timing (adjuvant versus neoadjuvant) of chemotherapy and radiation (yes/no) will be sequentially tested in the models for goodness of fit (Akaike Information Criterion) and included as appropriate.

**Aim 2: To determine whether decreased CNS glutamate correlates with improved symptoms of fatigue and cognition dysfunction.**

**Hypothesis 2:** Decreased glutamate in the basal ganglia will be associated with decreased fatigue and improved motivation and processing speed. Decreased glutamate in the dACC will be associated with improved executive function and memory performance.

Random intercept linear mixed models will be used to assess whether change in left or right basal ganglia or dACC glutamate predict change in fatigue scores or change in neurocognitive function over time. Models will be adjusted for relevant clinical covariates (including IDS-SR, PSQI, BAI) as indicated above. Separate analyses will be run for each behavioral outcome (MFI, PROMIS) as well tests of cognition (HVLT-R, TMT PASAT COWAT RT FTT, RTT, and DSST) and motivation (DDT, EEfRT, Subjective Value Task, Effort and Delay Task, Daily Assessment/Mobile App Task, Gamble Task, and Go No-Go Variant Task.). Type I errors as a result of multiple testing will be controlled by using a step down Bonferroni procedure.[68]

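### The Précis says the trial will determine whether lowering glutamate with riluzole reverses symptoms, but Section 10 compares the arms only on glutamate, so nothing prespecified supports that causal wording

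*Combined protocol and SAP*

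**What the plan says.** Section 2 (Précis) states a goal for symptoms: "We will also determine whether decreasing glutamate with riluzole will reverse inflammation-related fatigue and other symptoms including cognitive dysfunction and decreased motivation". The same section then says how symptoms will be handled: the assessments "will be conducted before and after treatment and correlated with the change in CNS glutamate".

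Section 5 words Aim 2 as a correlation: "To determine whether decreased CNS glutamate correlates with improved symptoms of fatigue and cognition dysfunction". Hypothesis 2, and the matching hypothesis at the end of Section 3, are also stated as associations.

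Section 10 has two model families. The Aim 1 mixed models "examine effects of group, time and their interaction on left and right basal ganglia glutamate or dACC controlling for baseline glutamate concentrations". The Aim 2 random-intercept models "assess whether change in left or right basal ganglia or dACC glutamate predict change in fatigue scores or change in neurocognitive function over time", with MFI and PROMIS as the fatigue outcomes. Their covariates are IDS-SR, PSQI, BAI and the list given under Aim 1. Treatment arm is not named in the model or among the covariates.

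Table 1 in Section 6 schedules self-report forms at both baselines and at Weeks 1, 2, 4 and 8. Its key lists "Self-Report Forms: IDS-SR, MFI, PROMIS-Fatigue, BAI, PSQI" among them. MRS is scheduled at Baseline 1, Week 1 and Week 8 only.

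**The concern.** *Reverse* is a causal word, and in this trial only the comparison of randomised arms gives a causal answer protected by the design. Section 10 makes that comparison for glutamate but not for any symptom. Change in glutamate is not itself randomised. Whatever drives it, such as illness course, sleep, inflammation or measurement conditions, may also drive fatigue.

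Two things are at stake. A positive Aim 2 association could be read as showing that riluzole relieves fatigue, which it would not show. And if an arm comparison of fatigue is wanted later, it would be post hoc, with the scale, MFI dimension, visit and baseline all open to choice.

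**Working it through.** **1. Which analyses contain the randomised comparison?**

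| Outcome | Where | Explanatory terms named | Arm comparison? |
|---|---|---|---|
| Basal ganglia and dACC glutamate | Section 10, Aim 1 | group, time, group by time, baseline | yes |
| MFI, PROMIS | Section 10, Aim 2 | change in glutamate, clinical covariates | none named |
| Cognition, motivation | Section 10, Aim 2 | change in glutamate, clinical covariates | none named |

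Sections 2, 3, 4, 5 and 11 specify no arm comparison of symptoms either. Section 11 sizes the trial on Aim 1 alone.

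**2. Can the Aim 2 association stand in for it?** A simulation with illustrative assumptions (20 per arm, one change score per patient, simple correlation in place of the Aim 2 model, two-sided 0.05) gives the share of trials that are significant:

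| Truth | Association | Arm difference in fatigue |
|---|---|---|
| Glutamate-fatigue correlation 0.5, riluzole affects neither | 92% | 5% |
| Same correlation, riluzole lowers glutamate by 0.5 SD, no effect on fatigue | 91% | about 5% |
| Riluzole lowers fatigue by 1 SD, unrelated to glutamate | 5% | 87% |

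The association can mislead in both directions. In the second row Aim 1 could succeed and Aim 2 would usually be positive, with no benefit on fatigue.

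**3. The plan's own power figure.** Section 11 gives d = 0.5 for glutamate with 40 patients, alpha 0.05 and power 0.80. It does not state sidedness. An unadjusted two-sided t test with 20 per arm has 34% power at d = 0.5. Baseline adjustment reaches 80% only at a correlation of about 0.84. The figure is not reproduced under these settings, but that is a separate matter and this point does not rest on it. The plan has no precision figure for fatigue.

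**4. Precision of an added fatigue comparison.**

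Inputs:
- Patients per arm: 20 (Section 5), or 16 if 20% of the 40 dosed are lost (40 × 0.8 = 32).
- Two-sided alpha 0.05.
- Correlation ρ between baseline and Week 8 score: not in the documents, so assumed, range 0 to 0.7.
- d in units of the unadjusted Week 8 SD.

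The Week 8 ANCOVA approximates the MMRM contrast: SE = √[(2/n)(1 − ρ²)], half-width = t(0.975) × SE, and power from the noncentral t (df = 2n − 3 with baseline adjustment, 2n − 2 without).

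- n = 20, ρ = 0: SE = √0.1 = 0.316; half-width 2.02 × 0.316 = 0.64.
- n = 20, ρ = 0.7: SE = √(0.1 × 0.51) = 0.226; half-width 2.03 × 0.226 = 0.46.

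| Per arm | Detectable d, 80% power (ρ 0 to 0.7) | 95% CI half-width, SD | Power at d = 0.5 |
|---|---|---|---|
| 20 | 0.91 to 0.65 | 0.64 to 0.46 | 34% to 58% |
| 16 | 1.02 to 0.73 | 0.72 to 0.52 | 28% to 48% |

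The Self-report Forms text cites minimal important differences of 10 points (MFI) and 3 to 5 raw points (PROMIS-Fatigue), without SDs. With 20 per arm and ρ = 0, 80% power for these needs an SD of at most 10/0.91 = 11 points on the MFI, and 3/0.91 = 3.3 to 5/0.91 = 5.5 points on PROMIS-Fatigue.

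**The case against.** The strongest reply is that the Précis asks a mechanism question about lowering glutamate, not whether riluzole works against fatigue. It says in the same paragraph that symptoms will be correlated with glutamate change. Section 4 makes the role of glutamate in symptoms the primary objective, and no aim or hypothesis promises an arm comparison of fatigue. On this view the problem is one causal verb in an abstract, and an efficacy comparison in a 40-patient mechanistic trial is optional.

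Much of this stands. A reader might infer that Aim 2 is analysed wrongly. It is not: the model matches its associational hypothesis. A reader might also infer that the trial sets out to test riluzole's efficacy against fatigue. The Précis sentence is narrower than that. The closing phrase of Section 5, "identifying peripheral biomarkers of risk as well as a novel treatment", is an aspiration and weak evidence of an efficacy claim. Nor would an arm comparison settle the mechanism. It estimates riluzole's total effect and cannot show that lowering glutamate produced it.

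The reply does not rescue the verb. A claim that lowering glutamate reverses symptoms is still causal, and an association with a variable that was not randomised does not establish it.

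A bleaker precision figure is also tempting: 10 per arm, by taking the unitless 20 in the Participants text of Section 6 from the 40 dosed under Randomization. The Participants text does not say this. It projects 120 × 0.5 = 60 eligible, and either 60 − 20 = 40 or 60 × 0.8 = 48 remaining, for 40 with analysable data. Ten per arm is only a stress case.

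**Conclusion.** The point holds as a gap between the Précis and Section 10. If the plan is followed exactly, the statement about reversing fatigue, cognitive dysfunction and reduced motivation has no prespecified randomised evidence behind it. The primary glutamate analysis is unaffected, and Aim 2 stands as a study of association. The plan should be changed, because the wording invites a causal reading and the fatigue data for a direct comparison are already being collected.

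That the gap exists follows from the text and needs no assumption. The precision figures rest on the assumed correlation and losses. Across that range only large effects on fatigue would be detected reliably. This is a reason to report an estimate with its interval, not a reason to leave the comparison out.

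**What to change.** 1. **In every case:** reword the whole Précis sentence, covering fatigue, cognition and motivation, so that the glutamate-symptom result is stated as an association. State in Section 10 that Aim 2 results are not evidence that riluzole relieves symptoms.

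2. **Add to Section 10** a prespecified secondary analysis in the Aim 1 model form: an MMRM of one MFI score and of PROMIS-Fatigue at Weeks 1, 2, 4 and 8, with arm, visit, arm by visit and a pre-treatment baseline score. Name the MFI score, because "The MFI assesses 5 dimensions of fatigue, including general fatigue, physical fatigue, mental fatigue, reduced activity, and reduced motivation". Name the baseline visit too, because both scales are collected at Baseline 1 and Baseline 2. Report the Week 8 riluzole-placebo difference with its 95% CI for each scale as an estimate, and say that it is riluzole's total effect on fatigue and does not show mediation by glutamate.

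The second step covers fatigue only. Statements about cognition and motivation stay associational under the first.

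The cost is a little more SAP wording and analysis, with no new data or visits. The fatigue estimate will be imprecise, and the report should say so.

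### Aim 2 does not name the pre-treatment value of the fatigue or cognitive outcome as a covariate, which costs precision if the response is a change score

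*Combined protocol and SAP*

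**What the plan says.** Section 10 (Statistical Analysis) plans random-intercept linear mixed models for Aim 2, to assess "whether change in left or right basal ganglia or dACC glutamate predict change in fatigue scores or change in neurocognitive function over time". On covariates it says: "Models will be adjusted for relevant clinical covariates (including IDS-SR, PSQI, BAI) as indicated above". The reference back is to the Aim 1 list of demographic, tumour and treatment variables, which are tried in turn and kept or dropped on AIC. Neither list contains baseline MFI, baseline PROMIS-Fatigue or a baseline cognitive score. The plan does not say at which visit IDS-SR, PSQI and BAI are taken for the adjustment.

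Aim 1, in the same section, does handle the outcome's own baseline: its models are fitted "controlling for baseline glutamate concentrations in separate analyses for each brain region".

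The baseline data exist. The key to Table 1 lists the self-report forms as including "IDS-SR, MFI, PROMIS-Fatigue, BAI, PSQI, Assessment of Pain level, PHQ-9", and Table 1 schedules these forms at Baseline 1, Baseline 2 and every later visit. MRS is done at Baseline 1, Week 1 and Week 8. Each cognitive test is given once before treatment, at either Baseline 1 or Baseline 2, and once at Week 8.

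**The concern.** When a change score is the response, its own baseline is usually one of its best predictors, because a high starting value tends to be followed by a larger fall through ordinary visit-to-visit variation. If baseline is not in the model, that predictable part counts as noise. Aim 2 can ill afford this: it has 40 women, no power statement of its own, many outcomes and a step-down Bonferroni correction.

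There is a second, smaller issue. MRS and the fatigue forms share the Baseline 1 visit. A fluctuation on that day that affects both enters both change scores with the same sign, and can produce an association that has nothing to do with a later fall in glutamate.

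**Working it through.** **Inputs from the documents.** 40 women, 20 per group. Two glutamate changes per woman (Week 1 and Week 8). Fatigue is measured at both of those visits; cognition is measured at Week 8 only. No SD or between-visit correlation is given for any outcome. The only power statement (Section 11) is for Aim 1, so there is no Aim 2 figure to reproduce.

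**Assumed.** Correlation r between baseline and follow-up fatigue of 0.3 to 0.7, with equal SDs unless stated.

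1. **One change score per woman.** In units of the outcome variance, the variance of raw change is 2(1 − r). After regression on baseline it is 1 − r². The ratio is (1 + r)/2, so the share removed is (1 − r)/2.
   - r = 0.3: 0.91/1.40 = 0.65, share 35%
   - r = 0.5: 0.75/1.00 = 0.75, share 25%
   - r = 0.7: 0.51/0.60 = 0.85, share 15%

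   The inverse ratios, 1/0.65, 1/0.75 and 1/0.85, correspond to 54%, 33% and 18% more women.

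2. **Narrower baseline spread.** With q the baseline SD over the follow-up SD, the share is 1 − (1 − r²)/(q² + 1 − 2rq). For q = 0.9 it is 28%, 18% and 7% at r = 0.3, 0.5 and 0.7. For q = 0.8 it is 22%, 11% and 2%. Simulated selection on a screening item, with r of 0.5 to 0.7 before selection, gives 7–22%.

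3. **Covariates that already carry baseline fatigue.** Suppose IDS-SR, PSQI and BAI are baseline values that explain a fraction R² of baseline fatigue and relate to follow-up only through it. The share left for baseline fatigue is (1 − r)²(1 − R²) / [(1 − r)²(1 − R²) + 1 − r²]. At r = 0.5 this is 0.1875/0.9375 = 20% for R² = 0.25, and 0.125/0.875 = 14% for R² = 0.5.

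4. **Two follow-ups with a random intercept.** Let v and c be the residual variance and the correlation between the two residuals, and g the correlation between the two glutamate changes. Information per woman on the slope is proportional to (2 − 2cg)/[v(1 − c²)]. Without baseline, v = 2(1 − r) and c = 0.5. With baseline, v = 1 − r² and c = r/(1 + r). At r = g = 0.5 the information is 1.5/0.75 = 2.0 without and 1.667/0.667 = 2.5 with, so the slope variance falls by 20%. At g = 0.5 the fall is about 30%, 20% and 11% for r = 0.3, 0.5 and 0.7. Over g from 0.3 to 0.7 it runs from 9% to 36%.

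5. **Power at n = 40, two-sided 5%, before the multiplicity correction.** Assume a change–change correlation of 0.3. By Fisher's z, √37 × atanh(0.3) = 1.883, and 1.883 − 1.960 = −0.077, so power is 47%. If glutamate change is unrelated to baseline fatigue, adjustment raises the correlation to 0.3/√((1 + r)/2) = 0.372, 0.346 and 0.325. With √36 in place of √37, power is 65%, 58% and 53%.

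   A simulation with further assumed inputs agrees in direction. It used 4,000 runs per setting, selection on a noisy screen, glutamate retest correlation 0.75, true glutamate-change SD 0.6, arm effect −0.5 and slope 0.8. Power rose from 39% to 54%, 52% to 63% and 69% to 76% for r = 0.3, 0.5 and 0.7. The mean estimated slope was 0.37 either way. With no link and no shared noise, both models rejected about 5% of the time.

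6. **Same-day noise shared by glutamate and fatigue, no true link.** With noise correlation 0.2–0.3 at baseline only, the 5% test rejected 7–11% of the time without baseline and 5–7% with it. With the same noise at both visits (glutamate retest correlation 0.75), it rejected 24–49% without and still 17–38% with.

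**The case against.** The strongest reply is that the model is never written out. A random-intercept model on repeated raw scores, with glutamate varying over time, is an ordinary way to relate two changes, and it uses the baseline score as an outcome row. The cognitive tests favour that reading: with one change per woman, a random intercept cannot be separated from residual error. The covariate list is also open-ended, so baseline fatigue might be admitted. This part stands to the extent that the omission is of a named term, not proof of a wrong model. It does not settle the matter, because the stated response is change in scores, and a covariate admitted through the Aim 1 route could be dropped on AIC.

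A reader might infer four stronger things that the documents do not support.

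- **That entry at fatigue of 4 or more builds in regression to the mean and so enlarges the loss.** Selection uses a single-item scale at screening. MFI and PROMIS-Fatigue are different instruments, measured afresh at Baseline 1 and Baseline 2. Selection tends to narrow the baseline spread, which shrinks the gain (step 2).
- **That 15–35% is a property of this trial.** It is (1 − r)/2 under assumed r and equal SDs. Allowing for a wider r and unequal SDs, a defensible range is roughly 0–40%.
- **That baseline adjustment cures false association from shared noise.** It nearly does if the noise is at baseline only. Both measures also share Weeks 1 and 8, and there it only reduces the problem (step 6).
- **That the trial's main test is affected.** Section 4 does describe the glutamate–symptom question as the primary objective, but Section 11 makes Aim 1 the primary hypothesis and sizes the trial on it.

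**Conclusion.** The point holds as a loss of precision that can be avoided at almost no cost. If Aim 2 is a change-score model, leaving out the outcome's baseline leaves about 15–35% of the outcome variance needlessly in the residual for r of 0.7 down to 0.3 with equal SDs. For the slope in a two-visit random-intercept model the corresponding figure is about 11–30% when the two glutamate changes correlate 0.5. Both figures are conditional on correlations that the documents do not give, and both fall if the baseline spread is narrow or the named symptom scales already carry baseline fatigue. If repeated raw scores are intended, baseline is already in use and the point reduces to writing the model down. Type I error is not at issue unless same-day noise is shared, and in that case adjustment is a partial remedy only.

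**What to change.** In Section 10, Aim 2, write out the model and add these terms:

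- **Outcome baseline.** In every Aim 2 model, include the pre-treatment value of that outcome (MFI, PROMIS-Fatigue or the cognitive score) as a fixed covariate, forced in and not subject to the AIC step. Use the Baseline 1 value where there is one, since it comes from the same visit as the baseline MRS, and otherwise Baseline 2.
- **Visit.** Include it as a fixed effect where there is more than one follow-up. That applies to fatigue at Weeks 1 and 8. Cognition has Week 8 only and needs no random intercept.
- **Baseline glutamate.** Preferably include this too.
- **Timing of IDS-SR, PSQI and BAI.** State the visit from which the adjusting values are taken.
- **Sensitivity analysis.** Report the unadjusted change-on-change result.

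The cost is a few sentences in the analysis section and one or two degrees of freedom per model, with no new data. One consequence should be stated in advance: glutamate change is not randomised, so adding baseline terms may move the estimated slope as well as its standard error. The sensitivity analysis lets the reader see how far.

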## **Baseline 2:**

**Rey Auditory Verbal Learning Test (RAVLT):** A test of verbal memory and learning using list learning that measures ability to use strategies to improve learning.

**Delayed Matching To Sample (CANTAB):**[44, 45] **Variables:** Response time, Discrimination (Hits/False Alarms). A measure of visual memory where subjects are asked to identify objects shown previously at various time points.

**Spatial Working Memory (CANTAB):**[46] **Variables:** Response time, Correct responses. A test of ability to remember spatial localization of objects presented previously

**Stroop Color and Word Test:** Subject is requested to name the color of a word both when the color of the ink matches the name of the color and when the color of the ink does not match the name of the color. Prolongation in reaction time and number of inaccurate responses during the name-ink color mismatch condition are measured.

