## **Week 8:**

Subjects will complete all neurocognitive testing from baseline 1 and baseline 2. Testing will be divided into two sessions with a break of at least ½ -1 hour.

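### The Aim 2 analysis list names nine tests the trial does not schedule and omits the whole Baseline 2 battery, so the memory part of Hypothesis 2 has no performance outcome to analyse

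*Combined protocol and SAP*

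**What the plan says.** For Aim 2, section 10 fits random intercept mixed models to ask whether "change in left or right basal ganglia or dACC glutamate predict change in fatigue scores or change in neurocognitive function over time". It runs a separate analysis for each outcome and names the outcomes in brackets. Fatigue is MFI and PROMIS. Cognition is given as "as well tests of cognition (HVLT-R, TMT PASAT COWAT RT FTT, RTT, and DSST" and motivation as "motivation (DDT, EEfRT, Subjective Value Task, Effort and Delay Task, Daily Assessment/Mobile App Task, Gamble Task, and Go No-Go Variant Task". Nothing marks either bracket as a set of examples. A step-down Bonferroni procedure covers the multiple tests, without a stated family.

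The tests given are set out in the Table 1 key and in the Neurocognitive Tests section. Baseline 1 has five: EEfRT, Finger Tapping, Trail Making, Digit Symbol and CANTAB Reaction Time. The second set is "Baseline 2 - Rey Auditory Verbal Learning Test (RAVLT), Delayed Matching To Sample (CANTAB), Spatial Working Memory (CANTAB), Stroop Color and Word Test". At Week 8, "Subjects will complete all neurocognitive testing from baseline 1 and baseline 2".

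Section 5 says of Aim 2 that "measures of motivation and psychomotor processing speed, attention, executive function, and memory will be assessed in the patients indicated in Aim 1". Hypothesis 2, in section 5 and again in section 10, ties lower dACC glutamate to better executive function and better memory performance.

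**The concern.** The outcome list and the schedule appear to describe two different batteries. If section 10 is followed as written, more than half of its outcomes will have no data, and four tests given twice to each participant will not be analysed. The worst effect falls on memory. HVLT-R, the only listed test that could serve as a memory outcome, is not scheduled, and the memory tests that are scheduled are not listed.

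An analyst who meets this at the end of the trial must choose replacement tests, the score to take from each, and the size of the multiplicity family. The Aim 2 model names no treatment-arm term, so its associations can be computed while the arms are still blinded. Blinding therefore does not stop those choices from following the data.

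**Working it through.** There is no stated figure to reproduce. The check matches the section 10 list against the tests in the Table 1 key and the test descriptions. Two readings favour the plan: RT and RTT both mean the CANTAB Reaction Time Task, and DSST means the Digit Symbol Task.

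**Step 1: match the lists.**

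| Outcome | In section 10 list | Given in the trial |
|---|---|---|
| MFI | yes | yes |
| PROMIS-Fatigue | yes | yes |
| Trail Making (TMT) | yes | yes |
| Reaction Time (RT/RTT) | yes | yes |
| Finger Tapping (FTT) | yes | yes |
| Digit Symbol (DSST) | yes | yes |
| EEfRT | yes | yes |
| HVLT-R | yes | no |
| PASAT | yes | no |
| COWAT | yes | no |
| DDT | yes | no |
| Subjective Value | yes | no |
| Effort and Delay | yes | no |
| Daily Assessment/Mobile App | yes | no |
| Gamble | yes | no |
| Go No-Go Variant | yes | no |
| RAVLT | no | yes |
| Delayed Matching To Sample | no | yes |
| Spatial Working Memory | no | yes |
| Stroop | no | yes |

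- Listed: 2 fatigue + 7 cognition + 7 motivation = 16. Not given: 3 cognition + 6 motivation = 9. 9/16 = 56%.
- With RT and RTT counted separately there are 17 outcomes: 9/17 = 53%, or 10/17 = 59% if one of the two is a different, unscheduled task.
- Neurocognitive tests only, without the two fatigue scales: 9/14 = 64%.
- Given but not listed: 4 of the 9 tests in the Table 1 key, 4/9 = 44%.

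**Step 2: look for a memory outcome.** The Neurocognitive Tests section describes RAVLT as verbal memory and learning, Delayed Matching as "A measure of visual memory where subjects are asked to identify objects shown previously at various time points", and Spatial Working Memory as recall of object location. All three are given and none is listed. Digit Symbol cannot stand in for them, because the protocol attributes only 4-5% of its variance to memory. The Baycrest Memory Scale is a self-report form, not a performance test, and it is not listed either. Memory performance tests both listed and given: 0 of 3.

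**Step 3: apply the Hypothesis 2 pairing.** The assignment of tests to domains is partly an assumption, in particular that Stroop is executive.

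- Basal ganglia (fatigue, motivation, speed): MFI, PROMIS, EEfRT, TMT-A, Digit Symbol, FTT, Reaction Time. All 7 of these collected outcomes are listed.
- dACC (executive function, memory): TMT-B, Stroop, RAVLT, Delayed Matching, Spatial Working Memory. Only 1 of 5 is listed (TMT-B).

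**Step 4: first step-down threshold, 0.05/m.** The plan does not define m, so these values are illustrative. They use one score per test, except where TMT is split.

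| Assumed family | m | 0.05/m |
|---|---|---|
| Paired, listed outcomes with data: 7 × 2 + 1 | 15 | 0.0033 |
| Paired, Baseline 2 battery restored: 7 × 2 + 5 | 19 | 0.0026 |
| All 11 outcomes × 3 regions | 33 | 0.0015 |
| The same with TMT-A and TMT-B separate: 12 × 3 | 36 | 0.0014 |

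**The case against.** The mismatch itself is not in dispute. Five points can be made against the weight put on it.

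- *The documents show only that the nine tests are unscheduled, and the schedule has stray text of its own.* Table 1 is headed for MRS controls, and the QIDS is marked for healthy controls, in a trial with no such arm. This stands in part: for PASAT, COWAT and the six motivation tasks, nothing states outright which side is out of date. However, the Table 1 key, the test descriptions and the Week 8 text agree on the same nine tests, and the Neurocognitive Tests section says the battery was built for these aims.
- *The model sentence refers to neurocognitive function in general, which could cover memory.* That sentence poses the question. The brackets say which analyses are run, and they leave out every memory test that is given. The written intention to study memory shows that the list is wrong, not that it is adequate.
- *The thresholds do not span the plausible families.* This is fair. Counting five MFI dimensions, two hands for finger tapping, and two measures each for Reaction Time, Delayed Matching, Spatial Working Memory and Stroop gives 13 × 2 + 8 = 34 paired tests (0.0015) or 21 × 3 = 63 crossed tests (0.0008). A per-region family of the 7 listed outcomes with data gives 0.05/7 = 0.0071. The wider range strengthens the case for defining the family.
- *Unnamed scores and the undefined family are separate gaps.* They are, and they add no weight to the mismatch. They belong in the same edit because the list is the only text that could set the size of the family.
- *Data-driven choice is speculative.* No section describes an Aim 2 analysis before unblinding. The claim is only that blinding would not prevent it.

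**Conclusion.** The concern holds. Of 16 listed outcomes, 9 (56%; 53% to 59% if RT and RTT are counted as two) have no scheduled test behind them. Of the 9 neurocognitive tests given, 4 (44%) are left out of the analysis, including all three performance tests of memory. As written, the memory part of Hypothesis 2 cannot be tested on performance data.

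The limits are clear. The list serves Aim 2 only, and section 11 bases the sample size on Aim 1. Seven listed outcomes can still be run, TMT-B keeps executive function testable, and no data are lost. The counts rest on the two favourable readings of abbreviations given above. The dACC ratio and the thresholds rest on assumed pairings and family sizes. This should be fixed before analysis, but it does not threaten the primary aim.

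**What to change.** Before MRS change data are analysed together with behavioural or cognitive data:

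1. Replace the section 10 list with MFI, PROMIS-Fatigue and the nine neurocognitive tests in the Table 1 key. The sponsor should confirm that none of the nine unscheduled tests is in use. If one is, the schedule needs correcting as well.
2. Name the score taken from each multi-score test, keeping TMT-A for processing speed and TMT-B for executive function.
3. State the baseline visit for each change score. Baseline MRS is at Baseline 1, while the restored tests have their baseline at Baseline 2.
4. The self-report forms include "PHQ-9, Single Item Screening Scale for Fatigue, Baycrest Memory Scale". Say whether the single-item fatigue scale and the Baycrest scale are Aim 2 outcomes.
5. Define the step-down Bonferroni family to match Hypothesis 2, for example the 19 paired tests above, or state that all regions are crossed with all outcomes.

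The cost is protocol and SAP wording. The tests are already given at baseline and Week 8, so no visit, test or participant burden is added.
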